### Response

Response, including evaluation of minimal residual disease (MRD), will be assessed by iwCLL guidelines for diagnosis and treatment of CLL (Hallek, 2008). The response rate based on the best response during the treatment period and the relative proportions in each response category will be examined. Distributions of the responses into the response categories (CR, CRi, nPR, PR, SD, PD) will be provided for each treatment arm. Response rates (CR+CRi+nPR+PR) together with confidence intervals will be provided for each regimen, both for the entire population and for the subgroups defined by the stratification factors.

### Duration of Response

Duration of response is defined as the time from the first visit where PR, CRi, or CR was documented to PD. Duration of response will be censored at the last date that the subject was known to be progression-free for: 1) subjects who have not progressed at the time of analysis; 2) subjects who have withdrawn consent or are lost to follow-up prior to documentation of progression.

For subjects who achieved at least a PR, Kaplan-Meier product limit methods will be used to estimate the survival functions for each treatment arm. Median duration of response along with two-sided 95% confidence intervals (CIs) may be estimated.

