### Progression-free Survival (PFS)

Progression-free survival is calculated as the time from randomization to the first documented progression or death due to any cause during or after the treatment period, whichever occurs first. The progression date will be assigned to the earliest time when any progression is observed without prior missing assessments. If withdrawal of consent or loss to follow-up occurs before documented progression or death, then these observations will be censored at the date when the last complete tumor assessments determined a lack of progression.

For subjects who do not develop progressive disease at the time of analysis, if the response from the last visit was 'not evaluable', the most prior visit date with complete evaluation indicating no progressive disease will be used as the censor date.

For subjects who received other anti-CLL or anti-neoplastic therapy before PD, the most prior visit date with complete evaluation indicating no progressive disease will be used as the censor date.

If a subject has 2 or more consecutive missing response assessments followed by PD, the prior assessment date with complete evaluation indicating no progressive disease will be used as the censor date.

If a subject died without PD while in study but there are 2 or more consecutive missing response assessments before death date, the prior assessment date with complete evaluation indicating no progressive disease will be used as the censor date.

Kaplan-Meier product limit methods will be used to estimate the survival functions for treatment arm. Median PFS along with two-sided 95% CIs will be estimated.

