### **Event-free Survival (EFS)**

Event free survival (EFS) is the interval between the start of treatment to the first sign of disease progression, or treatment for relapse, or death (whichever occurs first).

The censoring rules are the same as PFS, except that start of a new anti-CLL or anti-neoplastic therapy is considered an event.

Kaplan-Meier product limit methods will be used to estimate the survival functions for each treatment arm. Median EFS along with two-sided 95% CIs will be estimated.

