### **Time-to-Progression (TTP)**

TTP is defined as the time from randomization to the first documented progression. For subjects who do not progress during the study, TTP will be censored at the last adequate response assessment showing evidence of no disease progression. TTP is the same as PFS when there is no death. The same censoring rules for PFS applies except that death is not counted as an event.

Kaplan-Meier product limit methods will be used to estimate the survival functions for each treatment arm. Median TTP along with two-sided 95% confidence intervals (CI) will be estimated.

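### Duration of response ends only at progression, so a responder who dies without documented progression is censored and the death carries no penalty on this endpoint

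*SAP*

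**What the plan says.** SAP Section 11, Duration of Response, gives the definition: "Duration of response is defined as the time from the first visit where PR, CRi, or CR was documented to PD". Protocol 15.3 is worded the same way. Two groups are censored at the last date they were known to be progression-free: "1) subjects who have not progressed at the time of analysis", and "2) subjects who have withdrawn consent or are lost to follow-up prior to documentation of progression". The estimator follows: "For subjects who achieved at least a PR, Kaplan-Meier product limit methods will be used to estimate the survival functions for each treatment arm". A median with a 95% confidence interval is optional.

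The other time-to-event endpoints in SAP Section 11 each say what death does. For PFS: "Progression-free survival is calculated as the time from randomization to the first documented progression or death due to any cause". EFS also counts death as an event. For TTP: "The same censoring rules for PFS applies except that death is not counted as an event". Duration of response is the only progression-based endpoint whose text does not mention death.

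Nothing elsewhere fills the gap. The one efficacy sensitivity analysis in SAP Section 11 uses the investigator's assessment, and neither document plans a competing-risk analysis for this endpoint.

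**The concern.** A response can end because the disease progresses or because the patient dies. Under the wording, only the first ends it. A patient who dies in response fits the first censoring group, and Kaplan-Meier handles that patient like someone whose response is still running at data cut-off. The result answers how long until progression if nobody died. A reader of a duration-of-response table is likely to take it as time alive and in response.

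This matters in a trial whose primary objective is the safety of three starting-dose regimens. Deaths in response on one arm would not shorten that arm's duration of response, so the endpoint would not reflect a difference the trial is meant to show. The same death would normally end PFS and EFS, and a reader comparing the tables would find no explanation in the plan.

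**Working it through.** The documents give no duration-of-response figure to reproduce, so the check concerns the direction and likely size of the effect.

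**Direction.** With the same follow-up times used both ways, each death at a time when n responders are at risk contributes a factor (1 − 1/n) to the curve that counts death. Censoring the deaths removes those factors:

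S(PD only) = S(PD or death) ÷ product over deaths of (1 − 1/n).

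Each factor is below 1, so the PD-only curve is never lower and is higher from the first such death onwards. One qualification: the plan censors at the last progression-free date, which can precede the death by up to a visit interval (response visits are 28 days apart). Within that gap the curve can move slightly either way; after the death it lies above.

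**Number of responders.** With 35 per arm (SAP 6.1) and the relapsed/refractory response rates in Protocol 5.3.2:
- Lowest, 12%: 0.12 × 35 = 4.2.
- Highest, 57.7%: 0.577 × 35 = 20.2.
- In between, 32%: 0.32 × 35 = 11.2.

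A single death while all are still at risk raises the later curve by 1/(1 − 1/4) = 1.33 with 4 responders, 1/(1 − 1/11) = 1.10 with 11, and 1/(1 − 1/20) = 1.05 with 20.

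**Share of deaths.** The documents give no share of response-ending events that are deaths without progression. Two rough anchors exist, both for all patients rather than responders:
- Discontinuations in the earlier phase 1/2 study (Protocol 5.3.2.3), death 4% and progression 37%: 4/(4 + 37) = 9.8%.
- The 44-patient single-agent study (Protocol 5.3.2.1), 2 deaths and 17 progressions: 2/(2 + 17) = 10.5%.

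**Effect on the median.** Assume constant hazards, a fixed total hazard and a death share s. The PD-only hazard is (1 − s) times the total, so the median is multiplied by 1/(1 − s). Take 12 months for the true median of PD or death, borrowed from the responders' median PFS in Protocol 5.3.2.3:

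| s (assumed) | PD-only median, 12/(1 − s) | Lengthening | In response at 12 months (50.0% if death counts) |
|---|---|---|---|
| 5% | 12.6 months | 5% | 51.8% |
| 10% | 13.3 months | 11% | 53.6% |
| 20% | 15.0 months | 25% | 57.4% |
| 30% | 17.1 months | 43% | 61.6% |

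Only the 10% row has any anchor in the documents.

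**Small samples.** A simulation used the same hazards, administrative censoring at 60 months and 4,000 runs per setting. The median with deaths censored was never the shorter one. At a 10% death share it was strictly longer in 18% of runs with 4 responders, 41% with 11 and 66% with 20.

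**What additional deaths do.** At s = 10% the total hazard is ln2/12 = 0.0578 per month: 0.0520 for progression and 0.0058 for death. Double the death hazard and leave progression alone. The PD-only median stays at ln2/0.0520 = 13.3 months. The PD-or-death median falls from 12.0 to 12/1.1 = 10.9 months. The deaths leave no trace in the planned measure.

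**The case against.** The strongest reply is that the plan has two families of endpoints by design: progression-only (duration of response and TTP) and death-inclusive (PFS, EFS), with OS alongside. On that view the difference from PFS is intended, and deaths remain visible in PFS, EFS, OS and the death tables. It is true that a progression-only duration is a legitimate quantity, and calling the estimate too long presumes that time alive and in response is wanted. But TTP states that death is excluded and duration of response does not. The SAP never says outright that deaths are censored; that follows from its wording. Reading it instead as silent on death leaves a gap that also needs closing.

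A reader might go further and infer that a regimen with more deaths among responders would show a longer duration of response. The documents do not support this. If death and progression are independent, additional deaths leave the PD-only median unchanged, as shown above. It lengthens only if those who die were also closer to progression, for which there is no evidence here.

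Nor do the deaths in the Protocol's background show responders dying without progression. In the 44-patient study the two early infectious deaths are counted outside the responders (14 + 11 + 17 + 2 = 44). The two sepsis deaths in the phase 1/2 study, at days 37 and 94, were judged unrelated to study drug. The shortest time to response there was 2.8 months, about day 85 (2.8 × 30.4), so the first preceded any response, and the second patient is not said to have responded.

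PFS does not count every such death either: the SAP censors a death that follows two or more consecutive missed assessments.

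**Conclusion.** The point stands as a minor one. Followed literally, both documents censor a responder who dies without documented progression, and the Kaplan-Meier result then overstates time alive and in response whenever such a death occurs. A regimen with deaths in response pays no penalty on this endpoint, which is weaker than saying it gains from them.

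The size cannot be computed from the documents. About 11% on the median is an illustration: it assumes constant hazards, a fixed total hazard and a 10% death share taken from all-patient figures. With about 4 to 20 responders per arm, the actual effect could be nil or could turn on one patient.

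The primary endpoint is safety, and the SAP treats duration of response descriptively, so sample size is unaffected. Protocol 15.3 does plan a two-sided 0.05 log-rank test on it, which the SAP does not carry over; the event definition would matter for that test if it were run.

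**What to change.** In both Protocol 15.3 and SAP Section 11, end duration of response at progression or death from any cause, whichever is first. Reword the first censoring group to cover responders who have neither progressed nor died, and keep the other censoring rules. Since PFS has rules for new anti-CLL therapy and for deaths after missed assessments and this endpoint has none, add a clause saying whether those rules carry over.

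If progression-only is what the sponsor wants, say that death is not an event, as the TTP text does, and report the progression-or-death version beside it.

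The cost is a few words in each document; changing the SAP alone would create a discrepancy with the Protocol. No new data are needed, because death dates are already collected for OS. The downside is a somewhat shorter reported duration of response.

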### Time to Response

Time to response is calculated as the time from randomization to the first documented date of PR, nPR, CRi or CR based on iwCLL guidelines.

Summary statistics (mean, median, SDev, min, max) of time to response will be presented by treatment arm.

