Operationally the study will proceed as follows: Subjects will be randomized to one of the three treatment arms. The first interim analysis (toxicity only) will be performed once 18 subjects complete one 28-day cycle.

Subsequent

interim analyses will occur at 13-week intervals to monitor both combined toxicity and disease progression. Depending on the calculated posterior probability of toxicity and disease progression, any one of the three treatment arms may be dropped for excessive toxicity or progression rate.

Safety Analysis

All subjects who receive at least 1 dose of study drug will be included in the safety analyses. AEs, vital sign measurements, clinical laboratory information, and concomitant medications will be tabulated and summarized for each treatment arm during therapy. Subject incidence rates of all AEs (including serious, Grade 3, Grade 4, treatment-related [with and without discontinuation] and events requiring the discontinuation of investigational product), will be tabulated by system class, preferred term, and severity using MedDRA terms and by NCI CTCAE Version 3.0, with modifications recommended by the iwCLL guidelines for the diagnosis and treatment of CLL (Hallek, 2008), and by the Cairo-Bishop grading system for TLS. Time to first dose reduction will be summarized for each regimen.

Death and clinically important AEs (including TFR, TLS, second primary malignancies and thrombosis) will also be summarized.

All other measurements will be summarized using means, standard deviations, medians, minimum, and maximum. Graphical displays will be provided where useful in the interpretation of results.

Efficacy Analysis

Efficacy analyses will be performed on the intent-to-treat (ITT) population that includes all subjects randomized.

Response, duration of response, TTR, TTP, EFS, PFS, and OS will be summarized. The Kaplan-Meier procedure will be used to characterize the time-to-event curves in these analyses when there is censoring.

Exploratory Analysis

Pharmacokinetics Analysis

If the data are sufficient, noncompartmental PK parameters, such as T_{max} , C_{max} , AUC, CL/F, and $t_{1/2}$, will be estimated. Descriptive statistics will be provided for plasma concentrations and PK parameters. Lenalidomide concentration data obtained from all visits may be used to develop the population PK model. The relationship between pharmacokinetics and response (biomarkers or clinical outcomes as appropriate) will be explored.

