#### 5.1.4. Efficacy

Tumor response will be assessed according to the iwCLL guidelines for the diagnosis and treatment of CLL (Hallek, 2008), including complete response (CR), CR with incomplete bone marrow recovery (CRi), nodular partial response (nPR), partial response (PR), stable disease (SD), and PD. Evaluation of response will be performed after 3 cycles of therapy and every 4 weeks thereafter.

For those subjects who reach PR, CRi or CR, a CT scan of the neck, chest, abdomen and pelvis to assess lymphadenopathies will be performed at the PR and CR/CRi confirmation visits ( $\geq 8$  weeks to  $\leq 12$  weeks after all clinical and laboratory response criteria have been met for PR or CR/CRi). Those subjects whose response was down-graded based on the CT scan interpretation at the PR or CR/CRi confirmation visit will have the CT scan repeated 4 months later at the location where remaining disease has been documented, as long as clinical and laboratory response remains present to try to document further improvement.

For those subjects who reach CR or CRi, a bone marrow aspirate and bone marrow biopsy will be performed at the CR/CRi confirmation visit ( $\geq 8$  weeks to  $\leq 12$  weeks after all clinical and laboratory response criteria have been met). If the bone marrow is hypocellular, a repeat specimen should be obtained after 4 weeks, provided that the blood counts have recovered. If the bone marrow biopsy shows disease involvement (30% or greater lymphocytes, or nodules positive for B-CLL cells by immunohistochemistry), an additional bone marrow biopsy and aspirate will be taken 4 months later as long as clinical and laboratory response remain to document further improvement.

Minimal residual disease (MRD) will be evaluated for those subjects who reach CR or CRi. A peripheral blood and bone marrow aspirate sample will be collected for MRD analysis by flow cytometry at the CR/CRi confirmation visit.

- If peripheral blood and bone marrow are both MRD-positive, peripheral blood samples will be repeated and assessed up to 3 additional times at 8 week intervals to try to document MRD negativity in subjects who reach confirmed CR or CRi (see Follow-up MRD assessments).
- If peripheral blood is MRD-negative and bone marrow is MRD-positive, both peripheral blood and bone marrow should be retested for MRD negativity after  $\geq 12$  weeks. If this repeat bone marrow is MRD-positive, no further testing for MRD will be performed.

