## 6. GENERAL STATISTICAL CONSIDERATIONS

### 6.1. Sample Size

The sample size will be approximately 105 subjects, 35 per arm, barring early stopping. The original accrual rate is assumed to increase with time such that approximately 9-12 subjects will accrue in the first 3 months and a total of 41 to 55 subjects will accrue by 6 months with the remainder accruing by 60 weeks. Therefore, in addition to monitoring toxicity and progression, the accrual rate will be monitored.

The operating characteristics for the Bayesian Beta prior/schedule-administration adaptive design are given in protocol **Error! Reference source not found.**

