## 11. EFFICACY ANALYSIS

Efficacy analysis will be performed on the intent-to-treat population. Adjudicated response as will be used for these analyses. Sensitivity analysis will be done based on investigator's assessment.

Subgroup analysis might be done by duration of treatment (completed 3 cycles vs. withdraw treatment by Cycle 4 Day 1).

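### SAP 11 summarises time to response in responders only, so an arm that loses more subjects after the first response assessment can look faster while responding less at every time point

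*SAP*

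**What the plan says.** SAP section 11 (Time to Response) defines TTR as "the time from randomization to the first documented date of PR, nPR, CRi or CR" and then plans: "Summary statistics (mean, median, SDev, min, max) of time to response will be presented by treatment arm". It gives no censoring rule and no value for a subject who never responds.

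Three other places bear on this.

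- SAP 6.4.2 puts all efficacy analyses on the ITT population unless specified otherwise. The Duration of Response paragraph of SAP 11 states its restriction to subjects with at least a PR. The TTR paragraph states no restriction.
- The Efficacy Analysis part of the protocol synopsis says: "Response, duration of response, TTR, TTP, EFS, PFS, and OS will be summarized". It continues: "The Kaplan-Meier procedure will be used to characterize the time-to-event curves in these analyses when there is censoring".
- Elsewhere in SAP 11, duration of response, PFS, EFS, TTP and OS all get Kaplan-Meier estimates. For TTP the wording is: "Kaplan-Meier product limit methods will be used to estimate the survival functions for each treatment arm". TTR is the only endpoint with a time axis that does not.

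On timing, SAP 5.1.4 says: "Evaluation of response will be performed after 3 cycles of therapy and every 4 weeks thereafter".

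**The concern.** A mean or median of TTR can be calculated only from subjects who responded. Who responds depends partly on how long subjects remain assessable without progression. An arm that keeps losing subjects retains mainly its early responders. An arm that keeps its subjects goes on adding late ones. The first arm then shows the shorter TTR although at each time point fewer of its randomized subjects have responded.

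Unequal loss is plausible here. The arms differ in starting dose, and the adaptive design allows an arm to be dropped for toxicity or progression. The SAP also foresees early withdrawal: "Subgroup analysis might be done by duration of treatment (completed 3 cycles vs. withdraw treatment by Cycle 4 Day 1"). In the sponsor's earlier study (Protocol 5.3.2.3), median treatment duration was 3.1 months and median time to response 4.3 months (range 2.8 to 7.4; 6 responders of 52). The reasons for discontinuation there included progression (37%), withdrawn consent (15%) and death (4%). Loss and first response can therefore overlap in time. What is at stake is the reading of a named secondary endpoint across three starting doses.

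**Working it through.** The documents give no TTR figure to reproduce, so this is a check of direction and size under assumed rates.

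**Inputs from the documents.** First response assessment after 3 cycles, then every 4 weeks (SAP 5.1.4). Sample size: "The sample size will be approximately 105 subjects, 35 per arm, barring early stopping".

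**Assumptions.** Response hazard h = 0.06 per month from month 3 in both arms. Loss hazard d = 0.20 per month (arm B) or 0.05 (arm A), sustained from randomization. Loss means any event that ends the chance of a counted response.

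**Responder-only median.** Among responders, TTR minus 3 is exponential with rate h + d.
- B: 3 + ln 2 / 0.26 = 5.67 months
- A: 3 + ln 2 / 0.11 = 9.30 months

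Arm B looks 3.6 months faster.

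**Cumulative response in all randomized subjects.** At month t this is exp(−3d) × h/(h+d) × [1 − exp(−(h+d)(t−3))], where exp(−3d) is the proportion still assessable at month 3: 0.549 in B and 0.861 in A.

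| Time | B | A |
|---|---|---|
| 6 months | 0.549 × 0.125 = 7% | 0.861 × 0.153 = 13% |
| 12 months | 0.549 × 0.209 = 11% | 0.861 × 0.343 = 30% |
| Limit | 0.549 × 0.231 = 13% | 0.861 × 0.545 = 47% |

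Arm B responds less throughout but has the shorter TTR.

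**If the excess loss ends.** Let B's loss fall to 0.05 per month at month e. Among B subjects still assessable at month 3, the proportion responding by e is a = (0.06/0.26)(1 − exp(−0.26(e−3))). The proportion responding later is b = exp(−0.26(e−3)) × 0.06/0.11. The median is e − ln[1 − ((a+b)/2 − a)/b] / 0.11.
- e = 4: a = 0.053, b = 0.421, median 9.2 months; gap about 0.1
- e = 6: a = 0.125, b = 0.250, median 8.6 months; gap about 0.7

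**Same question on the 4-week visit grid.** First assessment at week 12, followed to week 104; in each interval loss is applied first, then response. Rates are again assumed.

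| Response per visit, A / B | Loss per 4 weeks, A / B | Responder mean, weeks, A / B | Responding by week 104, A / B |
|---|---|---|---|
| 8% / 8% | 3% / 15% | 38.5 / 26.1 | 63.4% / 22.5% |
| 8% / 8% | 3% / 15% in cycles 1–3, then 3% | 38.5 / 38.5 | 63.4% / 42.7% |
| 12% / 5% | 3% / 6% | 33.1 / 38.6 | 73.1% / 36.2% |

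Row 1 shows the distortion. Row 2 shows none, because the excess loss precedes any assessment. In row 3 the lower response rate outweighs the extra loss and B looks slower. In simulation of row 1 at 35 per arm, B had both the shorter observed mean and fewer responders in 94% of trials.

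**Kaplan-Meier with losses censored, row 1.** Eleven assessments fall in weeks 12 to 52, so both arms show 1 − 0.92^11 = 60.0% at week 52. The cumulative incidences are 48.5% and 21.0%. Censoring these losses hides the difference.

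**The case against.** The strongest reply is that this is a descriptive summary of an untested secondary endpoint. Response rates with confidence intervals are reported by arm on ITT, and Kaplan-Meier PFS, EFS and TTP stand beside them. A reader who sees a short TTR would also see the low response rate. No TTR test, and no arm-selection rule using TTR, is visible. This stands and limits the importance of the point. It does not remove it, because a final response rate does not put right a table that orders the arms wrongly on speed.

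Stronger readings that a reader might infer are not supported:

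- *The arm that loses subjects early will look faster.* Rows 2 and 3 of the visit-grid table are counter-examples. The excess loss must continue past the first assessment and outweigh any deficit in response rate.
- *Stopping drug for toxicity is such a loss.* Protocol 14.1 keeps these subjects on 28-day response visits until progression or new CLL therapy. The relevant losses are progression, death, withdrawal, loss to follow-up and new therapy.
- *Late first responses are documented by the 5.9-month median (range 1.6 to 18.3) in Protocol 8.1.4.* That is time to best response. The nearer figure is 4.3 months in Protocol 5.3.2.3, from only 6 responders.
- *The SAP plainly breaches the protocol.* The synopsis applies Kaplan-Meier only where there is censoring, and neither document defines censoring for TTR. The texts are unreconciled, and the synopsis does not itself support the remedy proposed here.

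**Conclusion.** The point holds in a conditional form. As planned, the TTR summary conditions on having responded, without saying so and despite the ITT rule. At equal response hazards, sustained excess loss after the first assessment shortens responder-only TTR while lowering cumulative response at every time point.

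The 3.6-month gap is not a forecast. It rests on an assumed fourfold difference in loss that never ends; with excess loss ending by month 4 to 6 the gap is about 0.1 to 0.7 months. The documents do not give loss rates by arm, so the size in this trial is unknown. The change is worth making because it is cheap, but nothing here touches the primary safety endpoint or any planned test.

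**What to change.** In SAP 11, add the cumulative incidence of first response (PR, nPR, CRi or CR) from randomization, by arm, in all ITT subjects. Treat progression, death and new anti-CLL therapy before response as competing events. Censor only for withdrawal, loss to follow-up or data cut-off, and show the number censored for each reason by arm, since heavy or unequal withdrawal would weaken the estimate. Give 95% confidence intervals at fixed times such as months 6 and 12.

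Keep the mean, median, SD, minimum and maximum as a description labelled as responders only, with n. Reconcile the TTR paragraph with the protocol synopsis. Kaplan-Meier that censors progression and death is not an adequate substitute.

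The cost is one paragraph and one figure; the event dates are already needed for PFS and EFS. Intervals will be wide: at 35 per arm and 30% cumulative response, ignoring censoring, the half-width is about 1.96 × √(0.30 × 0.70 / 35) = 15 percentage points.
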